A7. INTRODUCTORY SESSION OF ANTIMICROBIAL PRESCRIBING GUIDELINES MOBILE PHONE APPLICATION (MICROGUIDE)	58
A8. INTRODUCTORY (PAPER/APP GUIDELINES) SESSION REGISTRATION SHEET	59
A9. PRE-PRESCRIBING GUIDELINE SURVEY	60
A10. PRESCRIBER FEEDBACK SURVEY ON PAPER-BASED PRESCRIBING GUIDELINES	61
A11. PRESCRIBER FEEDBACK SURVEY ON MOBILE PHONE APP PRESCRIBING GUIDELINES	63
A12. ANTIMICROBIAL STEWARDSHIP (AMS) TRAINING	65
A13. ANTIMICROBIAL STEWARDSHIP (AMS) TRAINING SESSION REGISTRATION SHEET	66
A14. TIMELINES AND MILESTONES.....	67

Trial synopsis

Primary Objective	To compare the proportion of antimicrobial prescriptions adherent with prescribing guidelines delivered by mobile phone application (app) versus paper-based prescribing guidelines in both in- and outpatients in six general hospitals in Laos
Secondary objectives	
 1. To compare the change in antimicrobial defined daily doses (DDDs) after introduction of paper-based versus mobile phone app prescribing guidelines plus antimicrobial stewardship (AMS) training in both in- and out patients 2. To compare the change in proportion of patients receiving antimicrobials by the intravenous route between paper-based and mobile phone app prescribing guidelines + AMS training in both in- and out patients 3. To compare the AMS knowledge level of prescribers before and after prescribing guidelines delivered by mobile phone app and AMS training 4. To compare the prescriber satisfaction with/acceptability of paper-based prescribing guidelines versus mobile phone app prescribing guidelines 5. To compare antimicrobial costs before and after prescribing guidelines delivered by mobile phone app and AMS training in both in- and outpatient departments 6. To compare the proportion of patients admitted to hospital receiving an antimicrobial prescription before and after introduction of the paper-based prescribing guidelines; and the mobile phone app prescribing guidelines + AMS training
Methodology	
Study design	An open cohort stepped-wedge cluster randomized controlled trial 3-step trial (4-month intervals at each step) with a four-month pre-intervention period)
Study sites	Six general hospitals in Laos (two in the north (Luang Namtha and Xiengkhuang Provincial Hospitals), two in the centre (Mahosot Hospital and Vientiane Provincial Hospital) and two in the south (Savannakhet and Salavan Provincial Hospitals)
Study duration	16 months (four months preintervention period and 4-month interval between each step (three steps))
Sample size and power calculation	The sample size of six hospitals was estimated assuming 30% antimicrobial prescription adherence with the paper-based prescribing guidelines (reference), and assuming 0.05 intra-cluster correlation coefficient. This will have 80% power to be able to detect a 15% minimum difference in adherence after introduction of the mobile phone app prescribing guidelines (intervention) at a 0.05 significance level.
Randomization and blinding	Simple random sampling will be used to select the order (step) of interventions implementation for a group of hospitals (two hospitals per group and one group per step). Neither hospitals nor investigators will be blinded to the timing of intervention.
Intervention	A MicroGuide antimicrobial prescribing guideline mobile phone application and

	AMS training
Reference	Paper-based antimicrobial prescribing guidelines
Outcomes/Primary endpoint	The proportion of antimicrobial prescriptions adherent with prescribing guidelines delivered by mobile phone app versus paper-based prescribing guidelines at month 16 (12 months' exposure in each group)
Secondary endpoints	
 1. Total antimicrobial defined daily doses (DDDs) prescribed in mobile phone app versus paper-based groups after 12 months' exposure in each group 2. Proportion of patients prescribed antimicrobials by the oral route in mobile phone app versus paper-based groups after 12 months' exposure in each group 3. AMS knowledge level of prescribers prescribed in mobile phone app versus paper-based groups after 12 months' exposure in each group 4. Prescriber satisfaction/acceptability of the prescribing guidelines in mobile phone app versus paper-based groups after 4 months' exposure in each group 5. Total costs of antimicrobials prescribed in mobile phone app versus paper-based groups after 12 months' exposure in each group 6. Proportion of patients admitted to hospital receiving an antimicrobial prescription before and after introduction of the paper-based prescribing guidelines; and the mobile phone app prescribing guidelines + AMS training after 12 months' exposure in each group
Outcome measurement	
 • Point prevalence surveys (PPS) of hospital antimicrobial use • Prescriber questionnaires • AMS knowledge surveys of prescribers
Data management	
Open Data Kit (ODK) system will be used as data collection instrument. We will collect data on patients' characteristics, antimicrobial prescription status, the frequency of use of the antimicrobial prescribing guidelines (both paper-based and mobile app), AMS knowledge level of prescribers, acceptability of the guidelines and the cost of antimicrobial prescriptions in both groups.
 
All data will be kept securely, protected by password access with automatic daily backup.

Statistical analysis	A logistic mixed-effects regression model will be used to compare the proportion of antimicrobial prescription adherence measured cross-sectionally at month 0, 4, 8, 12 and month 16 after introduction of prescribing guidelines delivered by mobile phone application versus paper-based. The model will compare all wedges in the intervention from month 4 to month 16 with all wedges in the reference arm from month 0 to month 12. The duration of exposure of each hospital to the reference or intervention arm will be included in the model as interaction term with the study arm in order to assess whether the duration of exposure is the effect modifier. The model will consider the correlation among the outcomes' measurements from the same hospital (cluster) by adjusting for clustering in the model. Odds ratios and the corresponding confidence intervals will be obtained and reported.
Ethics	University of Health Sciences, Vientiane, Lao PDR and Oxford Tropical Ethics Committee (OxTREC), University of Oxford, United Kingdom

Trial insurance	Provided by University of Oxford
Dissemination	1/ Quarterly and annual reports (PPS dashboard and paper report) to participating hospitals, Lao Ministry of Health 2/ Publication in national and international journals 3/ Oral presentation/poster in both national and international levels
Sponsor	University of Oxford
Funder	Wellcome Trust of Great Britain

I. Introduction

Antimicrobial resistance (AMR) is the ability of microorganisms, including bacteria, fungi, viruses and parasites, to withstand exposure to antimicrobial medicines, such as antibacterial, antifungal, antiviral, anti-protozoal and anti-helminthic, so that the treatment becomes ineffective (1). Resistance can be acquired or intrinsic. Intrinsic resistance is the innate ability of bacteria to withstand the activity of some antimicrobial compounds whilst acquired resistance is the ability of bacteria to resist a particular antimicrobial compound which it was originally susceptible to. In a clinical setting, treating infections caused by bacteria having acquired novel resistance mechanisms is the main problem of AMR (2).

Antimicrobial Resistance - global situation

AMR is a major global public health concern with rising frequencies of AMR in key pathogens to key antimicrobials. The evidence suggests that this increase is accelerated by use, misuse or overuse of antimicrobials (3). AMR results in both direct consequences, such as longer duration of illness, increased mortality and prolonged stay in hospital, and indirect consequences such as reduced productivity caused by sickness and increased family, community and health system economic burden (4). O'Neill estimated that ~700,000 people die every year from drug resistant pathogens, including bacterial infections, HIV and malaria. If AMR continues to increase with no appropriate action being taken, this could contribute 10 million excess deaths and a cost of 100 trillion USD worldwide by 2050 (5). In 2019, Limmathurotsakul *et al.* argued that the estimation of the AMR global burden may have been distorted because of limitations in the methodological approaches (6). Since 2000, the number of antibiotics in development has fallen sharply. Many pharmaceutical companies have left the antibiotics market, stopping production and engagement in research and development (R&D), as the returns in profit of drugs given as short courses and with a short therapeutic life are far lower than those from drugs intended for lifelong use such as anti-hypertensive, or cholesterol-lowering drugs that do not fall to resistance (7). With drug-resistant infections potentially causing global economic damage on a par with the 2008 financial crisis, low-income countries could lose more than 5% of their GDP. AMR could push up to 28 million people into poverty, mostly in developing countries. Healthcare costs may increase by \$300 billion to more than \$1 trillion per year. A decline in global livestock production could range from 2.6% to 7.5% per year (8).

In order to address this major threat to global public health, there have been a number of

international initiatives. The Global Action Plan (GAP) to combat AMR was established by WHO in 2015, which consists of five strategies: 1) improving awareness and understanding of antimicrobial resistance; 2) strengthening knowledge through surveillance and research; 3) reducing the incidence of infection; 4) optimizing the use of antimicrobial agents; and 5) ensuring sustainable investment in countering antimicrobial resistance. The GAP mainly focuses on antibiotic resistance and provides a framework for National Action Plans to combat antimicrobial resistance over the next 5 to 10 years (9). In the same year, the global antimicrobial resistance surveillance system (GLASS) was established to support GAP. GLASS focuses on some specific microorganisms in specific samples such as: *Escherichia coli*, *Klebsiella pneumoniae*, *Acinetobacter baumannii*, *Staphylococcus aureus*, *Streptococcus pneumoniae* and *Salmonella* spp. in blood; *Escherichia coli* and *Klebsiella pneumoniae* in urine; *Salmonella* spp. and *Shigella* spp. in faeces; and *Neisseria gonorrhoeae* from urethral and cervical swabs (10). In February 2017, three global priority tiers of antibiotic-resistant bacteria were proposed by WHO to guide research, discovery and development of new antibiotics, including critical, high and medium priority pathogens (11).

Country profile of Laos

Lao PDR (Laos) is a land-linked country in Southeast Asia and bordered by China, Myanmar, Thailand, Cambodia and Vietnam. The majority (63%) of the population of ~6.77 million people live in rural areas and are predominantly dependent on farming. In 2013 the Gross National Income per capita was US\$ 4,570/year and life expectancy was 66 years. The World Bank reclassified Laos as a lower middle-income country in 2013 (9). From 2005 to 2015 Laos had one of the fastest growing economies in the world, with an average GDP growth rate of 7.8% per annum (12). Total health expenditure per capita increased from US\$29 in 2010-2011 to \$59 in 2015-2016 but total health expenditure as a proportion of GDP ranged from 2.4% to 3% during 2010 and 2016 (13). This is low compared to surrounding countries where the GDP expenditure is 6.5% in Thailand, 5.7% in Cambodia, and 7% in Vietnam, but is similar to that of Myanmar (2.3% of GDP) (12).

Healthcare system in Laos

The governmental healthcare system in Laos comprises three main administrative levels, including the Ministry of Health (MoH), Provincial Health Offices and District Health Offices. Based on data from the Curative and Healthcare Department in 2017, there are five central hospitals in Vientiane City and 17 provincial hospitals, 135 district hospitals (29 with ability of performing surgery and 106 unable to perform surgery) and 1,020 health centers (866 with ability to perform normal

vaginal delivery and 154 unable to perform normal vaginal delivery), country-wide (Curative and Healthcare Department, unpublished data 2017). There were 0.8-hospital beds per 1,000 population in 2010-2011. The most common issues found in the service delivery system are overcrowding of patients at central and provincial levels and underuse of district and community-level facilities (14). There are also a number of private international medical facilities in Vientiane, with links to Vietnam, China, France and the United Nations. There are also Thai government and private hospitals within easy reach of Vientiane and other towns in the Mekong Valley in Thailand. An Infection Prevention Control (IPC) committee was formed by MoH in 2008 and guidance on IPC at central and provincial hospitals was released in the same year. In 2014, IPC guidance for all healthcare levels was released. There are IPC committees in all central and provincial hospitals in Laos, as well as in some district hospitals.

In 2016, there were 20,484 health workers for the whole country (6,758,000 population) or 3/1,000 population. There were 2,716 physicians or 0.4/1,000 and 913 pharmacists or 0.13/1,000 population, and one medical school and one-degree level pharmacy programme within the [University of Health Sciences](#) in Vientiane (Ministry of Health, unpublished data 2016).

Limitations of laboratory services and clinical research infrastructure and capacity challenge the development of effective and evidence-based clinical and public health management strategies. In rural Laos, most treatment of infections is empirical, with basic laboratory testing such as Gram staining available at some provincial hospitals (15).

The national laboratory network structure in Laos is in line with the overall five-tiered organization of the national health system. Of these five laboratories, only two laboratories (National Center for Laboratory and Epidemiology (NCLE) and Microbiology Laboratory/Lao-Oxford-Mahosot Hospital Wellcome Trust Research Unit (LOMWRU) routinely culture bacteria and perform antimicrobial susceptibility testing. Some laboratories in central (Sethathirad Hospital and Mittaphab Hospital) and provincial hospitals are able to culture and identify some bacteria. The National TB Laboratory and Centre d'Infectiologie Christophe Mérieux of Laos (CICML) perform GeneXpert TB assays (16). Until mid-2019, both Mahosot Hospital and NCLE laboratories used disk diffusion according to Clinical & laboratory Standards Institute (CLSI) guidelines for most of their antibiotic susceptibility testing and before changing to European Committee on Antimicrobial Susceptibility Testing (EUCAST).

Antimicrobial resistance in Laos

Awareness of AMR is relatively recent in Laos and it is becoming a major public health concern. The main current concerns are Extended Spectrum Beta-Lactamase (ESBL) producing Enterobacteriaceae. ESBL producing *K. pneumoniae* and *E. coli* were first identified from the Mahosot Hospital Laboratory in clinical samples in 2000 and 2004, respectively. The frequency of ESBL-producing *E. coli* bacteraemia during 2004-2016 was 135/693 (19%), but the proportion of isolates producing ESBL increased 5-fold from 2004 2/28 (7%) to 2016 – 27/78 (35%). Whilst the proportion of *K. pneumoniae* producing ESBL was 39/284 (14%) between 2000-2016 in patients at Mahosot Hospital, there was no clear trend for an increase in ESBL producing *K. pneumoniae*, with levels varying from 3% to 41% over this period (Microbiology Laboratory/LOMWRU, unpublished data). Carbapenem resistance in *E. coli* was first identified in Laos in 2015 from a pus specimen from a patient admitted to Mahosot Hospital. Since then there have been three further isolates with the first carbapenem resistant *E. coli* isolated from blood in 2016 and 2017. All four isolates carried a New Delhi metallo- β -lactamase (NDM) gene (17). An analysis of 18 years of *Salmonella* Typhi bacteraemia data (2000-2018) in Laos showed 79% (712/898) were susceptible to all tested antimicrobials, 6.5% were multidrug-resistant and only 1% was fluoroquinolone resistant (18). Methicillin-resistant *Staphylococcus aureus* (MRSA) was also infrequent but it requires close monitoring; 18 years of bacteraemia data from Mahosot Hospital (2000-2018) only showed 2 patients with invasive MRSA infection. However, of concern, during 2017 and 2018, 71/426 (17%) *Staphylococcus aureus* isolates cultured from pus from clinical specimens at Mahosot Hospital were MRSA (Microbiology Laboratory/LOMWRU, unpublished data). There is scattered information on other GLASS pathogens available in Laos.

Hospital antimicrobial use in Laos

The Lao Food and Drug Department (FDD) is responsible for drug registration, licensing of pharmacies/drug companies/drug industries, and overseeing their distribution, import, drug quality control, domestic manufacture and also monitoring the supply chain. In 2016, 218 antibiotic active pharmaceutical ingredients (APIs) and combination APIs were registered by the Lao FDD; of these 38 (17%) were produced in Laos. The main sources of packaged antibiotics are from neighbouring countries such as Thailand and China (<http://www.fdd.gov.la/showContent.php?contID=48>).

In 2006, Keohavong *et al.* described that nearly half (47%) of Lao outpatients within 30 health

facilities investigated throughout the entire country were prescribed antibiotics for mild diseases such as simple diarrhoea or common colds (19). Few data on hospital antimicrobial use exist in Laos; at one northern provincial hospital, 51% of 1,095 patients (2008-2010) received antibiotics but only 7% of these received appropriate antibiotics (20). Nearly 70% of Lao doctors prescribed antibiotics at least once daily and stated that they had not received much information on appropriate antibiotic use during their careers. The doctors stated that they mainly prescribed antibiotics according to the National Standard Treatment Guidelines, advice from their peers, more experienced colleagues, pharmaceutical companies or the Internet. Doctors indicated a preference for local antibiotic guidelines written in Lao language to international ones in other languages (21).

The first hospital antibiotic use survey in Laos was conducted in 2017 using the Global Point Prevalence Survey methodology (LOMWRU, unpublished data). In 2018, five general hospitals across Laos participated in this survey, including two from the north, two from the centre and one from the south of Laos. Of 1,981 in-patient hospitals chart screened, 72% documented an antimicrobial (s) prescription, 43% patients received more than one antimicrobial, 98% were prescribed empirically and nearly half of them received antimicrobials for prophylaxis (LOMWRU, unpublished data). These hospital antimicrobial prescribing rates were much higher than rates (47%) reported in 2006 by Keohavong *et al.* (2006) (19).

Keohavong *et al.* (2019) interviewed 54 healthcare providers at outpatient departments (OPD) in five health facilities in Savannakhet Province, Laos, finding that 98% prescribed antibiotics based on patients' symptoms. The majority of them (91%) had heard about antimicrobial resistance but only 46.3% had been trained in the rational use of drugs. Medical records of 576 OPD patients under 5 years-old with upper respiratory tract infection (URTI) or common cold were screened for antibiotic prescription, 96% of URTI patients received antibiotic (s) and 5% for common cold patients. Of 405 patients given antibiotics, 395 (97.5%) received first line antibiotics (amoxicillin, ampicillin, erythromycin and penicillin V) based on Lao National Standard Treatment Guidelines. However, only a few of them used correct doses and durations based on these Guidelines (22).

There is evidence that multi-activity antimicrobial stewardship (AMS) programs could significantly reduce the proportion of therapeutic and prophylactic antibiotic prescriptions in both in- and outpatients from a study of a large patient population in China during 2010 and 2016 (23). Scheetz *et al.* (2009) also showed that combining antimicrobial stewardship with standard treatment of bloodstream infections had favourable cost-effectiveness compared to many other standard treatments of care (24). AMS programs have only been recently established in Laos. The first

training session on AMS to improve the rational use of antibiotic of Lao doctors, will be held in Vientiane City by Ministry of Health in mid-2020 with some pilot hospitals.

The need for antimicrobial prescribing guidelines

Lao Standard Treatment Guidelines (STG) were first established in 1998 and the latest edition was published in 2012. The guidelines are broad and cover a variety of issues such as medicines, surgery, and emergency medicines for both adults and children but do not include AMS or guidelines for treatment of many common infections. There are no approved Lao evidence-based infectious disease treatment guidelines, except for some specific diseases, e.g. malaria, TB, Sexually Transmitted Diseases (STDs) and HIV. LOMWRU conducted a small survey on the need for antimicrobial prescribing guidelines in Laos during November and December 2019; 70 Lao doctors from either central or provincial hospitals reported the main challenges to making decisions on the choice of antimicrobials were lack of access to a microbiology laboratory 31/70 (44%), no suitable antimicrobial prescribing guidelines 30/70 (43%) and poor availability of some antimicrobial agents 30/70 (43%). The majority of doctors used Lao treatment guidelines 58/70 (83%) and guidelines from neighboring countries 40/70 (57%) with a small proportion using European or US treatment guidelines 16/70 (23%). Only 17/70 (24%) had used any antimicrobial prescribing guideline/treatment guidelines delivered by a mobile application. Of these, 41% used the Medscape App (LOMWRU, unpublished data).

Antimicrobial prescribing guidelines have now been developed in country and are being adapted with the Ministry of Health based on AMR data from Laos, existing guidelines and international antimicrobial prescribing/treatment guidelines (e.g. WHO, CDC, NICE, Infectious Diseases Society of America (IDSA), Sanford). No antimicrobial use applications (apps) for the Lao PDR are available in English or Lao. Some 90% of Lao doctors from three provincial hospitals have smartphones (unpublished data) and apps are likely to be more attractive to physicians than bulky handbooks. Antimicrobial prescribing guidelines delivered by mobile phone app are now widespread in the world. Some evidence has suggested that antibiotic guidelines on a mobile phone app increased guideline adherence by prescribers, reduced unnecessary antibiotic use in hospital, reduced poor outcomes, improved quality of care and reduced antimicrobial consumption cost (25-27). Panesar *et al.* (2016) reported a survey on the use of MicroGuide smartphone application compared to pocket antimicrobial prescribing guidelines during a 3-month period at the University College London Hospital NHS Trust. Of 116 responses from pre-app survey questionnaires and 112 responses from

post-app survey questionnaires, the prescribing app was used more than pocket prescribing guides ($p < 0.01$). The majority of responses (>90%) agreed that the app was easy to navigate and it was the most appropriate means to access hospital guidelines. The app also improved their antimicrobial stewardship awareness (RR 6.8 (CI 2.1-21.7) (28). A study in three main hospitals of Imperial College Healthcare Trust, London demonstrated that when introducing mobile health to the setting with an existing antimicrobial stewardship program, the proportion of antimicrobial prescriptions adherence with the prescribing policy was significantly increased but there was no significant effect on antimicrobial prescription trends (29).

Study rationale

Although the severity of the AMR situation in Laos remains lower than elsewhere in Asia, misuse of antimicrobials is a major driver of resistance. This is a therefore an important opportunity for implementation of a simple technology, which may help reduce further worsening of the AMR situation. Antimicrobial prescribing apps are a promising tool to improve prescribing. However, there has been no evidence from trials to support whether the antimicrobial prescribing guidelines in the format of a mobile phone application are superior to conventional means (i.e. paper-based) in low- and middle-income countries (LMIC). This trial could have a significant impact in Laos and in other LMICs, and inform policy globally, by improving prescribing and hence reducing AMR.

II. Study objectives and hypothesis

Study objectives

Primary objective

To compare the proportion of antimicrobial prescriptions adherent with prescribing guidelines delivered by mobile phone application (app) versus paper-based prescribing guidelines in both in- and outpatients in six general hospitals in Laos

Secondary objectives

1. To compare the change in antimicrobial defined daily doses (DDDs) after introduction of paper-based versus mobile phone app prescribing guidelines plus antimicrobial stewardship (AMS) training in both in- and out patients

2. To compare the change in proportion of patients receiving intravenous antimicrobials route between paper-based and mobile phone app prescribing guidelines + AMS training in both in- and out patients
3. To compare the AMS knowledge level of the prescribers before and after prescribing guidelines delivered by mobile phone app and AMS training
4. To compare the prescriber satisfaction with/acceptability of paper-based prescribing guidelines versus mobile phone app prescribing guidelines
5. To compare antimicrobial costs before and after prescribing guidelines delivered by mobile phone app and AMS training in both in- and outpatient departments
6. To compare the proportion of patients admitted to hospital receiving an antimicrobial prescription before and after introduction of the paper-based prescribing guidelines; and the mobile phone app prescribing guidelines + AMS training

III. Methods

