3.6 Endpoints

Primary endpoint

The proportion of antimicrobial prescriptions adherent with prescribing guidelines delivered by mobile phone app versus paper-based prescribing guidelines at month 16 (12 months' exposure in each group)

Secondary endpoints

1. Total antimicrobial defined daily doses (DDDs) prescribed in mobile phone app versus paper-based groups of 12 months' exposure in each group

2. Proportion of patients prescribed antimicrobials by the intravenous route in mobile phone app versus paper-based groups of 12 months' exposure in each group
3. AMS knowledge level of prescribers prescribed in mobile phone app versus paper-based groups of 12 months' exposure in each group
4. Prescriber satisfaction/acceptability of the prescribing guidelines in mobile phone app versus paper-based groups of 4 months' exposure in each group
5. Total costs of antimicrobial prescribed in mobile phone app versus paper-based groups of 12 months' exposure in each group
6. Proportion of patients admitted to hospital receiving an antimicrobial prescription before and after introduction of the paper-based prescribing guidelines; and the mobile phone app prescribing guidelines + AMS training of 12 months' exposure in each group

Definitions of adherence to the guidelines

1. Full adherence with the guidelines = using correct antimicrobial agent (s) and correct dose based on the provided antimicrobial prescribing guidelines
2. Partial adherence with the guidelines = using correct antimicrobial agent (s) with incorrect dose based on provided antimicrobial prescribing guidelines
3. Non-adherence with the guidelines = using a different antimicrobial agent (s) compared to that suggested in provided antimicrobial prescribing guidelines

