measured cross-sectionally at month 0, 4, 8, 12 until month 16 after introduction of prescribing guidelines by mobile phone application versus paper-based (30). The model will compare all wedges in the intervention from month 4 to month 16 with all wedges in the reference arm from month 0 to month 12. The duration of exposure of each hospital to the reference or intervention arm will be included in the model as interaction term with the study arm in order to assess whether the duration of exposure is the effect modifier. The model will consider the correlation among the outcome's measurements from the same hospital (cluster) by adjusting for clustering in the model. Odds ratios and the corresponding confidence intervals will be obtained and reported. Tests of significance will be performed at 5% level. Analyses will be done using Stata 15.0 or higher. Likert scale analysis will be used to evaluate prescriber satisfaction with/ acceptability of paper-based compared to mobile phone app delivered antimicrobial prescribing guidelines. The satisfaction/acceptability scale will be assigned in six categories, including strongly agree=5, agree=4, neutral=3, disagree=2 and strongly disagree=1, no opinion/not use=0. Mann-Whitney test will be used to assess the differences between paper-based population and mobile phone app population. AMS knowledge level of prescribers will be assessed using questionnaires based on information in the prescribing guidelines. The overall proportion of correct answers in each time point will be compared (baseline, after paper-based guidelines (before AMS training and introduction of mobile phone app guidelines) and after AMS training and introduction of mobile phone app guidelines). Other factors such as extra AMR training program from hospital/MoH/other organizations, level of education and specialties of prescribers will also be taken into account.

Cost of antibiotic therapy will be calculated from the start date of treatment to the survey day. The unit costs for the antibiotics will be obtained from the [International Medical Product Price Guide](#).

Antibiotic defined daily dose (DDD) will be calculated using data (antibiotic agent, start date, dose and DDD of each antibiotic from www.whooc.no) from PPS in both IPD and OPD. Antimicrobial cost data from participating hospitals will also be collected each hospital pharmacy for comparison with international cost.

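### A difference in total DDDs between app and paper mixes dose per agent with numbers treated, so by itself it cannot show a change in how many patients or agents are treated

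*Combined protocol and SAP*

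**What the plan says.** Secondary objective 1 (synopsis and section II) reads "To compare the change in antimicrobial defined daily doses (DDDs) after introduction of paper-based versus mobile phone app prescribing guidelines", with AMS training added to the app, in both in- and outpatients. Section 3.6 turns this into the endpoint "Total antimicrobial defined daily doses (DDDs) prescribed in mobile phone app versus paper-based groups of 12 months' exposure in each group". No denominator is given there or in the synopsis.

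The calculation is in the Statistical analysis part of section 3.7: "Antibiotic defined daily dose (DDD) will be calculated using data (antibiotic agent, start date, dose and DDD of each antibiotic". The doses come from the point prevalence surveys of inpatients (IPD) and outpatients (OPD). No model for DDDs is named, and nothing says how a difference will be interpreted.

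Section 3.6 separates two levels of adherence by dose alone: "Full adherence with the guidelines = using correct antimicrobial agent (s) and correct dose based on the provided antimicrobial prescribing guidelines" and "Partial adherence with the guidelines = using correct antimicrobial agent (s) with incorrect dose based on provided antimicrobial prescribing guidelines". The primary endpoint, "The proportion of antimicrobial prescriptions adherent with prescribing guidelines delivered by mobile phone app versus paper-based prescribing guidelines at month 16", does not say which level counts.

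**The concern.** Prescribed dose enters the DDD calculation directly. The guidelines give doses for each disease (section 3.5), so better use of them can change dose with no change in how many patients or agents are treated.

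If doses under paper tend to be below the guideline, correcting them raises DDDs and can hide a fall in prescribing. If they tend to be above it, DDDs fall with nobody treated less. A report could then call a dose correction rising consumption, or a stewardship saving. A total without a denominator also moves with the number of patients who happen to be surveyed in each arm.

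**Working it through.** **1. No plan figure to reproduce.** The documents give no expected DDD level, difference or power for endpoint 1. The only power statement (section 3.3) concerns adherence and does not bear on this point.

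**2. What the total contains.** By identity:

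Total DDDs = patients surveyed × (agents / patients) × (agent-days / agents) × (DDDs / agent-days)

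The last factor carries the dose. The third equals 1 if only the survey day is counted, and exceeds 1 if days since the start date are accumulated. The plan does not say which. Appendix A2 (inpatients) records a start date; the Appendix A3 outpatient form has a stop date but no start date.

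**3. The dose factor alone.** Hold patients, agents and days fixed. Let s be the share of DDDs (valued at guideline dose) whose dose is corrected, and f the old dose divided by the guideline dose. Both are assumptions. Then

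relative change = 1 / [(1 − s) + s·f] − 1

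| s | f = 0.5 | f = 0.75 | f = 1.25 | f = 1.5 | f = 2 |
|---|---|---|---|---|---|
| 5% | +2.6% | +1.3% | −1.2% | −2.4% | −4.8% |
| 15% | +8.1% | +3.9% | −3.6% | −7.0% | −13.0% |
| 25% | +14.3% | +6.7% | −5.9% | −11.1% | −20.0% |

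- Example: s = 15%, f = 0.5 gives 1 / (0.85 + 0.075) = 1 / 0.925 = 1.081. A true 7.5% fall in volume would be fully masked, since 0.925 × 1 / 0.925 = 1.
- Cancelling: 15% misdosed, half at f = 0.5 and half at f = 1.5, gives 0.85 + 0.0375 + 0.1125 = 1.00, so no change.

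**4. The same mechanism with partial correction.** Suppose misdosing falls from 40% to 20% of agents (assumed).

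- At half dose, mean relative dose goes from 0.60 + 0.40 × 0.5 = 0.80 to 0.80 + 0.20 × 0.5 = 0.90, a ratio of 1.125. With a true 10% fall in agents, 1.125 × 0.90 = 1.0125, which shows as about +1%.
- At 1.5 times the dose, it goes from 1.20 to 1.10, a ratio of 0.917, or −8%.

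**5. The patients-surveyed factor.** Inpatient illustration, with section 3.2 beds as a stand-in for patients: centre 450 + 100 = 550, north 150 + 50 = 200, south 200 + 70 = 270. Figure 2 gives the three pairs, in order, 3, 2 and 1 app surveys and 1, 2 and 3 paper surveys (month 0 left out).

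- Centre, south, north: app 3×550 + 2×270 + 1×200 = 2,390 bed-surveys; paper 1×550 + 2×270 + 3×200 = 1,690. Ratio 1.41.
- North, south, centre: the two figures swap. Ratio 0.71.

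With identical prescribing per bed, a raw total could thus differ by +41% or −29% purely from the randomised order.

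**6. Which planned comparisons are free of dose?**

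- Endpoint 6 (proportion of patients with an antimicrobial prescription) is, but it names admitted patients only and counts any versus none. The Introduction reports that 43% of patients in the 2018 inpatient survey received more than one antimicrobial, so a fall in combination prescribing need not show there.
- Endpoint 5 (cost) also depends on the quantity prescribed, so it is no independent check.
- No planned arm comparison covers outpatient prevalence or agents per patient, although objective 1 covers both settings.

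**The case against.** The case against has real force.

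- **The plan does not rely on DDDs alone.** Endpoint 6 is dose-free. Section 3.5 also plans a before-and-after comparison of the proportion of prescriptions using 2019 data, and the Appendix A4 report tabulates patients on one, two or three or more agents for in- and outpatients. This stands, and it rules out saying that the plan has no dose-free measure. But Appendix A4 is hospital feedback, not an arm comparison, and the section 3.5 text names neither outpatients nor agents per patient.
- **A reader might infer that every dose correction moves DDDs and counts as a primary-endpoint success.** The documents do not support either half. A change in unit dose and frequency with the same daily total leaves DDDs unchanged, and corrections up and down can cancel. A correction counts in the primary endpoint only if adherent means fully adherent, which section 3.6 leaves open.
- **A reader might infer from the Introduction that dose correction will be large.** The cited outpatient study does say that "only a few of them used correct doses and durations based on these Guidelines". It concerned children under five with upper respiratory infection or common cold, was judged against the older national guidelines, and combined dose with duration. Here the paper arm already holds the dose recommendations, and section 3.5 says the app's content is the same. What matters is misdosing that persists under paper and that the app and training remove; the study does not address that.
- **DDDs are a legitimate measure of quantity.** This stands. Objective 1 does not claim to measure numbers treated, and no passage calls lower DDDs a success.

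**Conclusion.** The point holds as a limit on interpretation. An app-versus-paper difference in total DDDs combines dose intensity, agents per patient, patients surveyed and possibly days, so it cannot by itself be read as a change in how many patients or agents are treated. The stronger inference, that DDDs say nothing about antimicrobial use, is not supported: they still measure the amount prescribed.

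Over the assumed range (5% to 25% of prescribing corrected, from half to twice the guideline dose), full dose correction alone shifts DDDs by between −20% and +14%, and the net shift can be zero. These figures show what is possible, not what is expected; the documents give neither the rate nor the direction of dose errors in the six hospitals. The bed-survey ratios assume a literal raw total and bed numbers as a proxy for inpatients surveyed.

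The dependence on dose and the missing denominator need no such assumptions; they follow from the text. This is a secondary endpoint, and the change is a cheap improvement.

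**What to change.** Keep DDDs as the measure of quantity prescribed, but express them per 100 patients surveyed. Beside them, report by study arm and separately for IPD and OPD:

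- (a) antimicrobial agents per 100 patients surveyed, with the proportion of patients prescribed any antimicrobial extended from admitted patients to OPD;
- (b) DDDs per agent-day, labelled as dose intensity;
- (c) days of therapy to survey, where a start date exists.

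State that conclusions about the number of patients or agents treated rest on (a). Do not add a rule that a DDD change counts as consumption only when (a) changes: it would bar reporting a real fall in quantity from shorter courses. State also how days enter the DDD calculation in each setting.

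The cost is wording in the endpoint and analysis sections and a few more table rows. Agent, dose and doses per day are on the Appendix A2 and A3 forms, inpatient counts are on Appendix A1, and the outpatient denominator comes from the OPD logbook. No new data are needed. The drawback is a less compact endpoint than a single figure.
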